9.1 Statistical Hypotheses

This study is an exploratory PoC study with no formal confirmatory analysis. All analyses will be descriptive. No confirmatory hypothesis testing is planned, so no adjustment for multiple testing is necessary.

9.2 Sample Size Determination

Actively Enrolled Study Cohorts (Cohorts 1 to 4)

In total, 192 participants will be randomly assigned to study intervention with a ratio of 1:1:1:1 to Cohorts 1 to 4, such that approximately 180 evaluable participants are anticipated to be obtained assuming a drop-out rate < 10% as observed in other malaria studies. This will result in 45 participants per treatment cohort.

In order to investigate the time of protection of M5717 plus pyronaridine (see Section 2.1), it is important to show that with the highest dose of M5717 at least an effect comparable to Pyramax (pyronaridine+artesunate) over 63 days can be shown.

Within a clinical study by use of Pyramax for which results are reported in [Dabira 2022](#), 3 different dose regimens of Pyramax were compared with respect to number of patients with parasitemia over 63 days (1-, 2-, and 3-day regimen). For the 1 day regimen the same dose of pyronaridine as planned for this study was administered (540 mg/720 mg according to body weight) to asymptomatic individuals with *P. falciparum* infection. Out of 96 participants of the 1-day regimen arm 84.4% remained without parasitemia at Day 63. Since a slightly higher proportion of participants without parasitemia is expected for M5717 plus pyronaridine, a proportion of 87% will be assumed in the following.

In [Sukwa 1999](#) results of a randomized, double-blind, placebo-controlled field study to determine the efficacy of Malarone for prevention are reported. In this study, asymptomatic volunteers residing in a highly malarious area of Zambia were first treated with a 3 day treatment regimen of Malarone to clear all parasites (same approach as for Cohort 4 in this study). After liver and blood stage parasite cure, participants were randomized to receive daily treatment with either Malarone or Placebo over 70 days. In the Placebo group of 111 participants the proportion of participants without parasitemia at Day 70 was 63%.

Assuming, thus, cumulative % Survival for the Control (=natural infection cohort) and the highest dose group of M5717 plus pyronaridine combination to be 63% and 87%, a HR of 0.29 is expected (i.e. a 71% reduction of the risk for a parasitemia event in participants treated with the M5717 plus pyronaridine combination as compared to participants of Cohort 4). Basing the estimation on a Log-rank test given accrual and study duration to be 2 months each, the expected total number of events is 21 (which are expected to be distributed over both cohorts according to a HR of 0.29) and, with a total sample size of 90 participants, the estimated power is 80% with an assumed type 1 error of $\alpha = 0.05$.

Synthetic Control Cohort

It is planned to use external data as an additional cohort (Cohort 5) to compare with actively enrolled participants (for details on the data please refer to Section 3).

To minimize bias due to potential imbalances of confounding factors between external and study data, a PS matching will be used for balancing the multivariate baseline covariate data (the selection of covariates will be described in the IAP) across treatment groups. The PS matching will be done separately by treatment cohort since descriptive comparisons against the synthetic control arm will also be done by cohort. In order to end up with comparable cohort sizes at least approximately 35 participants should have a match per cohort. In case the number of identified matches falls below 35 the respective cohort will not be used for comparison to the synthetic

control arm from the external study. In case the number of matches is < 35 for all cohorts the use of the synthetic control arm will not be performed at all.

Matching of the external data will be performed after database lock and unblinding. Further details on the matching algorithm and the use of calipers will be defined in the IAP.

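### Protocol 9.2 pairs a Day 70 control figure with a Day 63 treatment figure; on a common Day 63 scale, assuming a constant control hazard, the stated 80% power becomes about 71%

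*Protocol*

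**What the plan says.** Protocol 9.2 (Sample Size Determination) takes its two survival inputs from two external studies.

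- **Control.** In a placebo-controlled prophylaxis study, parasites were first cleared with Malarone; then "participants were randomized to receive daily treatment with either Malarone or Placebo over 70 days". In the placebo group of 111, "the proportion of participants without parasitemia at Day 70 was 63" per cent.
- **Highest dose.** In the 1-day Pyramax arm of 96 participants, "84.4% remained without parasitemia at Day 63". A slightly better result is expected for M5717 plus pyronaridine, so "a proportion of 87% will be assumed in the following".

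The two figures are then used as one pair of cumulative survival proportions, with the "combination to be 63% and 87%, a HR of 0.29 is expected". The text adds a log-rank test, accrual and study duration of 2 months each and 21 expected events, and concludes that "with a total sample size of 90 participants, the estimated power is 80% with an assumed type 1 error of" 0.05, without saying whether alpha is one- or two-sided.

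The Brief Summary in Protocol 1.1 gives follow-up of up to 63 days (Day 64). Protocol 9.1 says the study is exploratory, that all analyses are descriptive and that no confirmatory test is planned. Neither the protocol nor the SAP describes moving the control figure from Day 70 to Day 63.

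**The concern.** Deriving one HR from two survival proportions requires both to refer to the same time. Here the control group has had a week longer to accumulate infections than the treated group, and longer than this trial will observe. That lowers control survival, exaggerates the contrast and makes the HR look smaller and the power higher than a like-for-like comparison would.

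At stake are the justification for 45 per cohort and the expectation set for the primary output, an HR with a 95% CI for each dose against Cohort 4. A reader of 9.2 will measure the observed HR and its interval against a 71% risk reduction and 80% power.

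A smaller point lies beside it: 63% and 87%, taken as they stand, do not give an HR of 0.29 or 21 expected events.

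**Working it through.** **Inputs (Protocol 9.2 unless noted).** Control 63% at Day 70; treatment 87%, anchored on Day 63; 45 per arm, 1:1; 21 events; HR 0.29; alpha 0.05, taken as two-sided in line with the 95% CIs in Protocol 9.4.1; follow-up 63 days (Protocol 1.1). Drop-out is already removed in going from 192 randomized to 180 evaluable.

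**Formulas.** Under proportional hazards, HR = ln(S_treatment)/ln(S_control) at a common time. Expected events d = 45 × [(1 − S_control) + (1 − S_treatment)]. Schoenfeld power = Φ(|ln HR| × √d / 2 − 1.96).

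**1. Reproducing the stated 80%.** With HR 0.29 and d = 21: |ln 0.29| = 1.238; 1.238 × √21 / 2 − 1.96 = 0.877; power 81%. Schoenfeld's required number for 80% at HR 0.29 is 4 × (1.96 + 0.842)² / 1.238² = 20.5, rounded up to 21. So the 21 that 9.2 calls expected equals the number required.

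**2. Using 63% and 87% as they stand.** HR = ln(0.87)/ln(0.63) = 0.301. Events = 45 × (0.37 + 0.13) = 22.5. Schoenfeld power is again 81%: the slightly weaker HR and the slightly higher event count cancel.

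**3. Control moved to Day 63, constant hazard assumed.**
- S_control = 0.63^(63/70) = 0.660
- HR = ln(0.87)/ln(0.660) = 0.335, a reduction of about 66%
- d = 45 × (0.340 + 0.13) = 21.2
- |ln 0.335| = 1.094; 1.094 × √21.2 / 2 − 1.96 = 0.56; power 71%

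**4. Same comparison by other methods (two-sided 0.05).**

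| Method | 63% vs 87% | 66% vs 87% |
|---|---|---|
| Schoenfeld | 81% | 71% |
| Simulated log-rank | about 77-78% | about 67% |
| Two proportions | 76% | 66% |
| Freedman | 72% | 63% |

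Each method loses about 9 to 11 points.

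**5. Treatment proportion giving 80% power against a 66% control, 45 per arm.** Schoenfeld: about 89% (at 89%, HR 0.280, 20.3 events, power 82%). Simulated log-rank with weekly detection: about 90% (77% power at 89%, 81% at 90%).

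**The case against.** The strongest reply is that the 66% is not in the documents. The formula ln(S1)/ln(S0) needs only proportional hazards; it does not require a constant baseline hazard, and 9.2 never states one. If no control infection fell in the last week of the source study, Day 63 survival would still be 63% and power about 78-81%. If infections were concentrated late, the loss would be larger than 10 points. This stands: 0.335 is a result under an assumption. It does not rescue 9.2, which needs the special case of essentially no control infections from Day 63 to Day 70 and gives no support for it.

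Three further replies also stand.

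- **Sampling error.** With 111 participants, a simple 95% CI for 63% is 63 ± 1.96 × √(0.63 × 0.37/111), about 54% to 72%. The 3-point shift lies well inside it, and 87% is itself a judgement. Restated figures should be rounded.
- **Sidedness.** Alpha's sidedness is not given. One-sided Freedman also reproduces the stated power (81% at HR 0.29 and 21 events) and would fall to about 74%. The direction is the same.
- **Consequence.** No decision rule depends on power, and the reported CI will show the precision achieved.

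A reader might go further in two ways that the material does not support. One is to set a simulated 66-67% against the stated 80%; simulation gives only 77-78% before any adjustment, so that gap includes a change of method. The other is to read the 2 months in 9.2 as 61 days and quote an HR of 0.346. That moves the control but leaves 87% at Day 63, which is the same mismatch again. With both arms at 61 days (66.9% and 87.4%) the HR is 0.335 and Schoenfeld power 70%.

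**Conclusion.** The concern holds as a minor point. The stated HR and power rest on survival figures from different time points. On a common Day 63 scale the expected HR is about 0.335 instead of 0.29, about 21 events are expected, and power falls from 81% to 71% by the method that reproduces the protocol. This assumes a constant control hazard, two-sided 0.05, and 45 evaluable participants per arm.

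The discrepancy in HR and events (0.30 and 22.5 against 0.29 and 21) needs no hazard assumption but leaves power unchanged on its own.

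A reader might infer that the trial is too small and must be enlarged. The documents do not support that: Protocol 9.1 plans no confirmatory test, so what is affected is the sample-size rationale and the expected precision of the HR.

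**What to change.** Reword Protocol 9.2, with no change in N, endpoint or analysis:

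- Put both survival inputs at Day 63. Say that the control source reports Day 70 only and that the Day 63 value assumes a constant hazard.
- Give control about 66%, highest dose 87%, HR about 0.34 (about a 66% reduction), about 21 expected events and power about 70% with 90 participants.
- Name the power method and state whether alpha is one- or two-sided.
- If a detectable effect is added, label it by method: 80% power needs about 89% without parasitemia by Schoenfeld, or about 90% by simulated log-rank.

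The cost is a short text change and a less favourable stated power. If the control source's Day 63 estimate can be obtained, it should replace the interpolated 66% and the figures should be recalculated.

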9.3 Analysis Sets

The Analysis Sets are specified in [Table 3](#).

Table 3 Analysis Sets

Analysis Set	Description
FAS	The FAS will include all randomized participants. Participant will be analyzed according to the treatment assigned at randomization as per the Intention-to-Treat (ITT) principle.
SAF	All participants who were administered any dose of any study intervention. Analyses will consider participants as treated.
PK Analysis Set	All participants, who receive 1 dose of study intervention, have no clinically important protocol deviations or important events affecting PK, and provide ≥ 1 measurable postdose concentration. Participants will be analyzed per the actual study intervention they received. All PK analyses will be based on this analysis set.

9.4 Statistical Analyses

This Section provides a description of the statistical methods to be used to analyze efficacy, safety, and other endpoints. Prior to locking the database, a detailed IAP will be finalized. All details of the statistical analyses not covered by the following sections will be described in the IAP.

Unless otherwise specified, the FAS will be the primary analysis set for all efficacy analyses. The SAF will be used for all safety data reporting.

Continuous variables will be analyzed by displaying the number of available observations, mean, SD, median, lower and upper quartiles, and minimum, and maximum values. Where applicable, 95% CIs will be provided.

Ordinal variables will be summarized by frequency tables, including the number of available observations, median, and lower and upper quartiles.

Qualitative variables will be analyzed by frequency tables.

9.4.1 Efficacy Analyses

In [Table 4](#) only main analyses are described for the primary and secondary efficacy endpoints. Additional sensitivity and subgroup analyses will be planned in the IAP.

Table 4 Summary of Main Statistical Analyses – Efficacy

Reference #	Category	Statistical Analysis
Primary		
1 – Time to parasitemia since negative blood smear after treatment	Main	Time to parasitemia since negative blood smear after treatment will be analyzed. HRs will be estimated from a Cox Proportional Hazards model separately for the 3 dose groups of M5717 plus pyronaridine compared to Cohort 4 together with 95% CIs. Additionally, Kaplan-Meier curves will be provided to descriptively compare the time to parasitemia between the treatment groups.
Secondary		
2 - Incidence of parasitemia	Main	The proportion of participants with parasitemia will be estimated from Kaplan-Meier curves and displayed by treatment group together with 95% CIs.
CCI		

9.4.1.1 Efficacy Analyses Related to Primary Objective

Per ICH E9(R1), Addendum on Estimands and Sensitivity Analysis in Clinical Trials (November 2019), the primary estimand targeting the primary objective is defined by the following attributes:

- **Variable (endpoint):** The primary endpoint is the time to parasitemia since parasite clearance (randomization) defined as the time without a positive blood smear.
- **Treatment:** Intervention of interest is single dose of either 60 mg M5717 + 720 mg pyronaridine (≥ 65 kg) or 540 mg pyronaridine (≥ 45 to < 65 kg), 200 mg M5717 + 720 mg pyronaridine (≥ 65 kg) or 540 mg pyronaridine (≥ 45 to < 65 kg), or 660 mg M5717 + 720 mg pyronaridine (≥ 65 kg) or 540 mg pyronaridine (≥ 45 to < 65 kg).
- **Target population:** The target population is defined as the population of patients targeted by the clinical question. In this exploratory PoC study the target population is defined by adult and adolescent patients with asymptomatic *P. falciparum* malaria.
- **Strategies for handling ICEs:** A composite variable strategy, i.e. the primary endpoint is considered as failure (positive blood smear) is applied if participants take rescue medication after intake of study intervention or if they discontinue the study due to malaria induced death. In case participants experience any event that effects the absorption of the study intervention (e.g. vomiting within the study intervention absorptive period of 2 times median T_{max}), a treatment policy strategy is applied as to which the treatment effect is estimated regardless of the ICE. An on-treatment strategy is considered for participants with documented intake of antibiotics or other prohibited medication that impacts the treatment effect (e.g. drug with antimalarial activity) at any timepoint or if participants die from other reasons than malaria, i.e. the time parasitemia since parasite clearance is censored at the time of antibiotics or prohibited medication intake and at the time of death, respectively.

- **Population-level summary:** The population-level summary of the primary endpoint is the HR for the different dose groups in comparison to the natural incidence of infection as measured in Cohort 4. HRs together with 95% CIs will be estimated from Cox Proportional Hazard models. Details of the models and potential factors or covariates to be included will be described in more detail within the IAP.

9.4.1.2 Efficacy Analyses Related to Secondary Objectives

For the secondary endpoints incidence of parasitemia (positive blood smear), and incidence of PCR-adjusted parasitemia (new infections and recrudescence), similar estimand attributes as for the primary endpoint apply. For incidence of gametocytemia, a treatment policy strategy will be applied in case of intake of antibiotics or prohibited medications and in case of malabsorption of study treatment. Events of death due to malaria and to other causes will be handled according to a composite variable and on-treatment strategy, respectively.

9.4.2 Safety Analyses

All safety analyses will be performed on the Safety Analysis set. The safety analyses are described in [Table 5](#).

AEs will be classified using the most recent MedDRA version at time of the analysis to determine SOC, PT, and SMQs.

Table 5 Summary of Main Statistical Analyses – Safety

Reference #	Category	Statistical Analysis Methods
Secondary		
6 - Incidence, severity, and seriousness of TEAEs, treatment-emergent study intervention related AEs, as per CTCAE v5.0	Main	Frequency and percentage of participants by SOC and PT.

TEAEs are defined as AEs which started at or after the administration of IMP (study treatment) or which started prior to the first administration of IMP but worsened after the dose intake, until the last scheduled assessment will be regarded as treatment-emergent, but before established rescue antimalarial treatment is administered, if required. Treatment-related AEs are those rated by the Investigator as “definitely”, “probably” or “possibly” related. All AEs will be documented, and will include the Investigator term, the preferred term, start, and end date of AE, duration (days), severity, drug relationship, action taken, and outcome. Liver signals (AT increase, TB increase) and CNS signals will be considered AESIs and specific follow-up will be performed, through laboratory surveillance, and a specific physical examination at specific visits during the follow-up.

Abnormal laboratory findings and other abnormal investigational findings should not be reported as SAEs unless they are associated with clinical signs and symptoms, lead to treatment discontinuation, or are considered otherwise medically important by the Investigator.

Examples of medically important findings include:

- Requirement for treatment or any other therapeutic intervention.
- Necessity for further diagnostic evaluation (excluding repetition of the same procedure to confirm the abnormality).
- Association with clinical signs or symptoms that may have a significant clinical impact, as determined by the Investigator.
- Clinically significant changes (as assessed by the Investigator) of any laboratory parameter throughout the study (compared to the last assessment prior to trial treatment).

Note: if the abnormal results were already present at baseline with the same severity, it will be recorded as medical history.

9.4.3 Other Analyses

Demographics and medical history will be analyzed descriptively.

The PK and CCI [REDACTED] are described in Table 6.

Details on the PK and **CCI** analyses will be in the IAP that will be finalized before database lock. **CCI**

Details on the analyses performed in the optional DMFA substudy (reduction of infectivity of gametocytes, mosquito infectivity parameters, and gametocyte parameters) are provided in [Appendix 2](#). The results of the substudy will be reported separately.

Table 6 **Summary of Statistical Analyses – PK and **CCI****

Reference #	Category	Statistical Analysis Methods
Secondary		
7 – PK	PK parameters (in Section 8.4)	Summary statistics of PK parameters will be provided. For PK parameters no estimand attributes have been defined. Detailed descriptions of PK analyses will be part of an annex to the IAP. All PK analyses will be performed on the PK Analysis Set.
CCI		

Appendix 1 Abbreviations

ACT	artemisinin-based combination therapy
ADME	absorption, distribution, metabolism, and excretion
AE	adverse event
AESI	adverse events of special interest
AIDS	acquired immunodeficiency syndrome
ALP	alkaline phosphatase
ALT	alanine aminotransferase
AST	aspartate aminotransferase
AT	aminotransferase
CFR	Code of Federal Regulations
CHMP	Committee for Medicinal Products for Human Use
CI	confidence interval
CIOMS	Council for International Organizations of Medical Sciences
CNS	central nervous system
COVID-19	Corona Virus Disease 2019
CRF	case report form
CRO	Contract Research Organization
CSR	clinical study report
CT	computerized tomography
CTCAE	Common Terminology Criteria for Adverse Events
CTFG	Clinical Trial Facilitation Group
CYP	cytochrome P450
DDI	drug-drug interaction
DILI	drug-induced liver injury
DMC	Data Monitoring Committee
DMFA	direct membrane feeding assay
DRE	disease-related events
DRO	disease-related outcome

ECG	electrocardiogram
eCRF	electronic case report form
EDC	electronic data capture
EMA	European Medicines Agency
EOS	end of study
FAS	full analysis set
FIH	first in human
GCP	Good Clinical Practice
Hb	hemoglobin
HIV	human immunodeficiency virus
HR	hazard ratio
HRT	hormonal replacement therapy
IAP	integrated analysis plan
IB	Investigator's Brochure
IC ₅₀	half maximal inhibition concentration
IC ₉₉	Approximately 100-fold greater than IC ₅₀ concentration
ICE	intercurrent event
ICF	informed consent form
ICH	International Council for Harmonization
IEC	Independent Ethics Committee
IMP	investigational medicinal product
INR	international normalized ratio
iPT	intermittent preventive therapy
IPTsc	intermittent preventive treatment in school aged children
IRB	Institutional Review Board
ITT	intent-to-treat
IUD	intrauterine device
IUS	intrauterine hormone-releasing system
LAM	lactational amenorrhea method
LFT	liver function test
MDA	mass drug administration

MedDRA	Medical Dictionary for Regulatory Activities
MRI	magnetic resonance imaging
NASH	Nonalcoholic fatty liver disease
NCE	new chemical entity
NCI-CTCAE	National Cancer Institute Common Terminology Criteria for Adverse Events
NCT	National Clinical Trial number
NRTI	nucleoside reverse transcriptase inhibitor
NSAID	Nonsteroidal anti-inflammatory drug
PACTR	Pan African Clinical Trials Registry
PCR	polymerase chain reaction
PD	pharmacodynamic(s)
PDMC	Post discharge malaria chemoprevention
PeEF2	plasmodium eukaryotic translation elongation factor 2
PGx	pharmacogenetic
PK	pharmacokinetic(s)
PMC	perennial malaria chemoprevention
PoC	Proof-of-concept
POCBP	participant of childbearing potential
PS	Propensity Score
PT	preferred term
QTcF	corrected QT interval by Fridericia' formula
QTL	quality tolerance limit
RDT	rapid diagnostic test
RT-qPCR	real-time quantitative reverse transcription PCR
SAE	serious adverse event
SAF	safety analysis set
SARI	serotonin antagonist and reuptake inhibitor
SARS-CoV-2	severe acute respiratory syndrome coronavirus 2
SBP	systolic blood pressure
Scr	Screening

SD	standard deviation
SMC	seasonal malaria chemoprevention
SmPC	Summary of Product Characteristics
SMQ	Standardized MedDRA query
SoA	Schedule of Activities
SOC	System Organ Class
SOP	Standard Operating Procedure
SPAQ	sulfadoxine-pyrimethamine plus amodiaquine
SUSAR	suspected unexpected serious adverse reactions
TA	Therapeutic Area
TB	total bilirubin
TEAE	treatment-emergent adverse event
ULN	upper limit of normal
WHO	World Health Organization

[figure not shown]
**Appendix 2 Substudy to Evaluate the Efficacy of the Combination M5717
Plus Pyronaridine Versus Malarone to Reduce Post-treatment
P. Falciparum Transmission (DMFA Substudy)**

Table 7 Schedule of Activities – DMFA Substudy (Cohorts 1 to 4)

Assessments & Procedures	Outpatient/ Inpatient ^a		Outpatient				Notes
Visit Number	Screening and Visit 1 ^a	Visit 2 ^a	Visit 3	Visit 4	Visits 5 to 12	Visit 13	^a Visit 1 and 2: Participants randomized to Cohorts 1 to 3 will remain in the hospital or vicinity of the site for 24 hours.
Timepoint	Day 1	Day 2	Day 3	Day 4	Week 2 to 9 (weekly visits starting at Day 8)	EOS (last visit) Week 10, Day 64 ^b	
Visit Window					± 1 day	± 2 days	
Informed consent and eligibility for the substudy	X						
Venous blood sampling for DMFA	X ^c	X	X	X	X ^d	X ^d	^c Predose and 1 h after the first dose. ^d DMFA will only be performed if the participant is infectious to mosquitoes on any of the 2 preceding feeding days.
Venous blood sampling for DMFA after MACS	X ^e	X					^e Predose and 1 h after the first dose.
Venous blood sampling for gametocyte assessments	X ^f	X	X	X	X	X	^f Predose and 1 h after the first dose.

DMFA = direct membrane feeding assay, EOS = end of study, MACS = magnetic cell sorting

CCI

Substudy Design

This substudy is an ancillary study to the main study. Additional blood samples will be taken for participants enrolled into the substudy (see [Table 7](#)).

Substudy Population

Individuals who were randomized to Cohorts 1 to 4 of the main study will be approached to identify if they are willing to be involved in this substudy. Participation in this substudy is entirely voluntary. A participant's decision to participate or to not participate in the substudy will not affect their participation, care, or treatment in the main study.

Participants are eligible to be included in the substudy if in addition to the eligibility criteria of the main study (see [Section 5.1](#) and [5.2](#)) all of the following criteria apply.

Inclusion criteria:

1. *P. falciparum* gametocyte carriage confirmed by microscopy with a minimum gametocyte density of 2 per 500 WBC (~32 per μ L) at the time of randomization in the main and substudy

Exclusion criteria:

1. Administration of immunoglobulin and/or any blood products within the 3 months preceding the study participation
2. Any finding that would in the Investigator's opinion interfere with study participation

Objectives and Endpoints of the Substudy

Mosquito infectivity will be assessed at 3 levels: the mean number of oocysts in a sample of mosquitoes (i.e. oocyst density), the proportion of mosquitoes in a given assay infected with any number of oocysts (i.e. mosquito infection rate), and the relation between infectivity of the study participants and infectivity of mosquitoes. These different aspects of mosquito infectivity are translated into primary and secondary/CCI as described in below table. All analyses of mosquito infectivity will be conducted on all participants who are infectious at baseline (i.e. with a minimum gametocyte density of 2 per 500 WBC (~32 per μ L at randomization).

Objectives	Estimands/Endpoints	Ref. #
Primary		
To assess the intra-individual reduction of infectivity of gametocytes (in terms of mosquito infection rate) following administration of Malarone alone or M5717 plus pyronaridine (single dose regimen) at Day 2 (24 hours) compared to pretreatment (Day 1)	
Endpoint: Percent reduction in the mosquito infection rate of mosquitoes fed with Day 2 (24 hours post treatment) blood sample and mosquitoes fed with Day 1 (pretreatment) blood sample. The mosquito infection rate is defined by the proportion of mosquitoes in an assay infected with any number of oocysts.
 
Population-level summary: Arithmetic mean by dose cohort with 95% CI
	S1
Secondary		
To assess the intraindividual reduction of infectivity of gametocytes (in terms of mosquito infection rate) following administration of Malarone alone or M5717 plus pyronaridine (single dose regimen) at all feeding timepoints post treatment compared to pretreatment (Day 1)	
Endpoint: Percent reduction in the mosquito infection rate of mosquitoes at different feeding timepoints and mosquitoes fed with Day 1 (pretreatment) blood sample. The mosquito infection rate is defined by the proportion of mosquitoes in an assay infected with any number of oocysts.
 
Population-level summary: Arithmetic mean by dose cohort with 95% CI
	S2
To assess the intraindividual reduction of infectivity of gametocytes (in terms of oocyst intensity) following administration of Malarone alone or M5717 plus pyronaridine (single dose regimen) at all feeding timepoints post treatment compared to pretreatment (Day 1)	
Endpoint: Difference in the mean number of oocysts in a sample of mosquitoes at different feeding timepoints and mean number of oocysts in a sample of mosquitoes fed with Day 1 (pretreatment) blood sample.
 
Population-level summary: Geometric mean by dose cohort with 95% CI
	S3

Objectives	Estimands/Endpoints	Ref. #
To assess differences in gametocyte prevalence following administration of Malarone alone or M5717 plus pyronaridine (single dose regimen) at all feeding timepoints post treatment compared to pretreatment (Day 1)	Endpoint: Difference in gametocyte prevalence at all feeding timepoints determined by molecular assays and gametocyte prevalence at Day 1. Gametocyte prevalence is defined by the percentage of study participants that are carriers of gametocytes. Population-level summary: Arithmetic mean of differences in proportions by dose cohort with 95% CI	S4

Substudy Assessments and Procedures

Mosquito feeding assays

Membrane feeding will be performed to determine infectivity to locally reared female *Anopheles coluzzii* mosquitoes, as described in detail in online protocols ([Goncalves 2017](#), [Reuling 2017](#)).

The blood sample for feeding will be obtained prior to study intervention administration where applicable. On Day 1 and Day 2, additional heparinized blood will be taken and enriched using the MACS gametocyte enrichment method ([Reuling 2017](#)). The gametocytes enriched blood will be used for duplicate feeding assay.

Oocyst assessments

Fully fed mosquitoes will be kept at 27°C to 29°C with access to glucose solution for approximately one week (6 – 8 days) prior to dissection and assessment for the presence and density of oocysts by 2 independent microscopists blinded to study arms. Infected guts will be stored for later PCR confirmation of oocysts

CCI

A series of horizontal black bars of varying lengths, with the longest bar at the bottom.

A solid black rectangular bar located at the bottom of the slide, spanning most of the width. It appears to be a decorative element or a placeholder for content.

A solid black rectangular bar is positioned at the bottom of the slide, spanning most of the width. It is likely a placeholder for a logo or a decorative element.

Blinding

Parasitologists and laboratory personnel performing the microscopy, the membrane feeding assays and PCR will be blinded with respect to dose cohorts to minimize bias.

Statistical Considerations for the Substudy

This substudy is fully exploratory. All analyses conducted will be of descriptive nature. Details on the planned analyses will be described in the IAP together with the description of planned analyses for the main study. Definitions of estimands and intercurrent events were not considered for this substudy, since endpoints are based on measures of the DMFA based on blood samples of the participants. Study participants are not directly involved in any measurement for the substudy.

Substudy References

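### DMFA substudy endpoint S3 is a difference in mean oocyst counts but is summarised by a geometric mean, which fails once a cohort contains a negative or zero difference

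*Protocol*

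**What the plan says.** The table under Objectives and Endpoints of the Substudy (Protocol Appendix 2) sets out S3 as follows.

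- Objective: "To assess the intraindividual reduction of infectivity of gametocytes (in terms of oocyst intensity"), at every feeding timepoint after treatment against Day 1.
- Endpoint: "Difference in the mean number of oocysts in a sample of mosquitoes at different feeding timepoints", set against the corresponding Day 1 mean. The text does not say which is subtracted from which.
- Summary: "Geometric mean by dose cohort with 95% CI".

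No ratio, log transformation, added constant or rule for zeros is given. S1 and S2 are percent reductions summarised as "Arithmetic mean by dose cohort with 95% CI". S4, the only other endpoint defined as a difference, is also summarised by an arithmetic mean.

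Appendix 2 defers analysis details to the SAP (the Integrated Analysis Plan). The visible SAP text does not mention the DMFA substudy, oocysts or S3: the scope statement in Section 6 does not name the substudy, and the visible part of Section 7 lists no change to S3.

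**The concern.** A difference can be positive, zero or negative. A geometric mean is an average on the log scale and is meant for positive quantities, so the endpoint and its summary do not fit together.

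S3 is the only visible endpoint that measures oocyst intensity rather than the proportion of mosquitoes infected. If the text stays as it is, whoever analyses the substudy must choose the sign, the scale and the treatment of zeros, possibly after seeing the data. As shown below, that choice can change the reported figure several-fold.

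**Working it through.** The documents give no sample size, power or result for S3, so there is no planned figure to reproduce. The check is whether the stated summary exists for the values that the plan allows.

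**1. Requirement.** For participant differences d, the geometric mean is exp(mean(log d)), and its usual interval comes from the same logs. Every d must be above 0. A negative d has no log. A zero has log minus infinity; with no negatives present the geometric mean is then 0 and the interval is undefined.

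**2. Can such values occur?** Three statements in Appendix 2 bear on this.

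- Oocyst density is "the mean number of oocysts in a sample of mosquitoes (i.e. oocyst density"). It is not restricted to infected mosquitoes, so it can be 0.
- The analysis population is "participants who are infectious at baseline (i.e. with a minimum gametocyte density of 2 per 500 WBC"...). This is a gametocyte criterion, not a mosquito result, so a Day 1 oocyst mean of 0 is possible. Such a participant gives a zero difference if the later feed is also 0, and an increase if it is not.
- From Day 8, "DMFA will only be performed if the participant is infectious to mosquitoes on any of the 2 preceding feeding days" (Table 7). The plan therefore expects some feeds with no infected mosquitoes.

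**3. Illustration (assumed values, not from the documents).**

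| Participant | Day 1 mean | Later mean | Later − Day 1 | Day 1 − later |
|---|---|---|---|---|
| 1 | 4.0 | 0 | −4.0 | 4.0 |
| 2 | 1.2 | 0 | −1.2 | 1.2 |
| 3 | 0 | 0 | 0 | 0 |
| 4 | 8.5 | 1.0 | −7.5 | 7.5 |
| 5 | 0.3 | 0.5 | 0.2 | −0.2 |

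- Later minus Day 1: three negatives and one zero, so 4 of 5 logs do not exist as finite numbers. The geometric mean is undefined.
- Day 1 minus later: one negative and one zero. The geometric mean is still undefined.
- Day 1 minus later without participant 5: (4.0 × 1.2 × 0 × 7.5)^(1/4) = 0, with no log-scale interval.
- Arithmetic mean of all five: −12.5/5 = −2.5, or +2.5 with the sign reversed. It exists either way.

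**4. How often would it exist?** Take Day 1 minus later, and let each participant independently have probability q of a zero or negative reduction. The summary and its interval exist only if all n values are positive, with probability (1 − q)^n. Both q and n are assumptions.

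| q | n = 5 | n = 10 | n = 20 |
|---|---|---|---|
| 5% | 77% | 60% | 36% |
| 10% | 59% | 35% | 12% |

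**5. Other readings.** Suppose S3 means the geometric mean of the oocyst means at each timepoint. In the example the later means contain zeros, so their geometric mean is 0 and the interval is again undefined. Suppose instead that it means a ratio of later to Day 1. Zeros then require an added constant c, giving exp(mean(log[(later + c)/(Day 1 + c)])):

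| c | 0.01 | 0.1 | 0.5 | 1 |
|---|---|---|---|---|
| Ratio | 0.083 | 0.205 | 0.369 | 0.466 |

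For c = 1 the product of the five ratios is (1/5)(1/2.2)(1/1)(2/9.5)(1.5/1.3) = 0.0221, and its fifth root is 0.466. Across these constants the answer changes by a factor of 0.466/0.083 = 5.6.

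**The case against.** The strongest reply starts from the objective, which speaks of a reduction. Read as Day 1 minus timepoint, responders give positive values, and if everyone in a cohort responds the geometric mean exists. That is a fair reading, and it rules out a stronger inference that a reader might draw, that S3 breaks down precisely in the participants in whom the drug works. That follows only from timepoint minus Day 1, and the protocol does not fix the direction. The reply does not save the summary, however: one participant with an increase makes it undefined, and one with zero oocysts at both feeds removes its interval.

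A second reply is that each participant's difference can be computed. This is correct. Only the cohort summary and its interval fail, not the endpoint itself.

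A third is that the details may be written elsewhere. Appendix 2 and the SAP both contain redactions, and Protocol Sections 9.4.3 and 9.4.4 give the substudy its own final analysis and report. The lack of a repair can therefore be stated only for the visible text. Even so, a definition elsewhere would have to replace the protocol wording rather than add detail to it.

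Finally, the substudy is optional, exploratory and descriptive. That limits the consequence, but it does not make the statistic computable.

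**Conclusion.** The stated summary for S3 does not suit the stated endpoint. In either direction of subtraction it is undefined with any negative value; with zeros and no negatives it equals 0 and has no log-scale interval. The plan's own definitions make such values foreseeable. Since S4 pairs a difference with an arithmetic mean, a drafting mismatch in S3 is the likely explanation.

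A reader might also infer that participants without a reduction would be left out and transmission blocking thereby overstated. The documents do not support this. No exclusion rule of that kind appears, and the mosquito infectivity analyses are to include all participants who meet the gametocyte criterion. Nor is a zero difference the same as non-response: a participant with no oocysts on Day 1 and none later had nothing to reduce.

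The numerical size rests on assumed participant values, failure probabilities and cohort sizes, because the documents give none. The effect is limited to one secondary endpoint of an optional substudy. No main-study conclusion depends on it.

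**What to change.** In Appendix 2, or in the analysis plan that governs the substudy:

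1. State the direction as Day 1 minus timepoint, so that a reduction is positive.
2. Replace the S3 summary with the arithmetic mean of the within-participant differences by dose cohort at each feeding timepoint, with a bootstrap 95% CI. This is consistent with S4.
3. State that participants with zero or negative differences are kept.

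If a relative measure is preferred, use a geometric mean ratio only with the zero rule or constant fixed before the data are seen, and show how the result changes with it.

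If redacted text or a separate substudy plan already defines S3 differently, align the protocol wording with it. The arithmetic-mean option costs a few lines of text and no new data. The ratio option also needs a reasoned choice of constant, which is more than an editorial change.
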